**APPENDIX 5. SF-36 HEALTH SURVEY UPDATE**

This survey asks for your views about your health. This information will help keep track of how you feel and how well you are able to do your usual activities. *Thank you for completing this survey!*

For each of the following questions, please mark an  in the one box that best describes your answer.

**1. In general, would you say your health is:**

Excellent	Very good	Good	Fair	Poor
▼	▼	▼	▼	▼
 1	 2	 3	 4	 5

**2. Compared to one year ago, how would you rate your health in general now?**

Much better now than one year ago	Somewhat better now than one year ago	About the same as one year ago	Somewhat worse now than one year ago	Much worse now than one year ago
▼	▼	▼	▼	▼
 1	 2	 3	 4	 5

**3. The following questions are about activities you might do during a typical day. Does your health now limit you in these activities? If so, how much?**

Yes, limited a lot	Yes, limited a little	No, not limited at all
▼	▼	▼

- a Vigorous activities, such as running, lifting heavy objects, participating in strenuous sports .....  1 .....  2 .....  3
- b Moderate activities, such as moving a table, pushing a vacuum cleaner, bowling, or playing golf.....  1 .....  2 .....  3
- c Lifting or carrying groceries .....  1 .....  2 .....  3
- d Climbing several flights of stairs .....  1 .....  2 .....  3
- e Climbing one flight of stairs .....  1 .....  2 .....  3
- f Bending, kneeling, or stooping .....  1 .....  2 .....  3
- g Walking more than a mile.....  1 .....  2 .....  3
- h Walking several hundred yards .....  1 .....  2 .....  3
- i Walking one hundred yards .....  1 .....  2 .....  3
- j Bathing or dressing yourself .....  1 .....  2 .....  3

**4. During the past 4 weeks, how much of the time have you had any of the following problems with your work or other regular daily activities as a result of your physical health?**

All of the time	Most of the time	Some of the time	A little of the time	None of the time
▼	▼	▼	▼	▼

- a Cut down on the amount of time you spent on work or other activities.....  1 .....  2 .....  3 .....  4 .....  5
- b Accomplished less than you would like .....  1 .....  2 .....  3 .....  4 .....  5
- c Were limited in the kind of work or other activities .....  1 .....  2 .....  3 .....  4 .....  5
- d Had difficulty performing the work or other activities (for example, it took extra effort) .....  1 .....  2 .....  3 .....  4 .....  5

**5. During the past 4 weeks, how much of the time have you had any of the following problems with your work or other regular daily activities as a result of any emotional problems (such as feeling depressed or anxious)?**

All of the time	Most of the time	Some of the time	A little of the time	None of the time
▼	▼	▼	▼	▼

- a Cut down on the amount of time you spent on work or other activities.....  1 .....  2 .....  3 .....  4 .....  5
- b Accomplished less than you would like .....  1 .....  2 .....  3 .....  4 .....  5
- c Did work or other activities less carefully than usual .....  1 .....  2 .....  3 .....  4 .....  5

**6. During the past 4 weeks, to what extent has your physical health or emotional problems interfered with your normal social activities with family, friends, neighbors, or groups?**

Not at all	Slightly	Moderately	Quite a bit	Extremely
▼	▼	▼	▼	▼
 1	 2	 3	 4	 5

**7. How much bodily pain have you had during the past 4 weeks?**

None	Very mild	Mild	Moderate	Severe	Very severe
▼	▼	▼	▼	▼	▼
 1	 2	 3	 4	 5	 6

**8. During the past 4 weeks, how much did pain interfere with your normal work (including both work outside the home and housework)?**

Not at all	A little bit	Moderately	Quite a bit	Extremely
▼	▼	▼	▼	▼
 1	 2	 3	 4	 5

**9. These questions are about how you feel and how things have been with you during the past 4 weeks. For each question, please give the one answer that comes closest to the way you have been feeling. How much of the time during the past 4 weeks...**

All of the time	Most of the time	Some of the time	A little of the time	None of the time
▼	▼	▼	▼	▼

- a Did you feel full of life? .....  1 .....  2 .....  3 .....  4 .....  5
- b Have you been very nervous? .....  1 .....  2 .....  3 .....  4 .....  5
- c Have you felt so down in the  
dumps that nothing could  
cheer you up? .....  1 .....  2 .....  3 .....  4 .....  5
- d Have you felt calm and  
peaceful? .....  1 .....  2 .....  3 .....  4 .....  5
- e Did you have a lot of energy? .....  1 .....  2 .....  3 .....  4 .....  5
- f Have you felt downhearted  
and depressed? .....  1 .....  2 .....  3 .....  4 .....  5
- g Did you feel worn out? .....  1 .....  2 .....  3 .....  4 .....  5
- h Have you been happy? .....  1 .....  2 .....  3 .....  4 .....  5
- i Did you feel tired? .....  1 .....  2 .....  3 .....  4 .....  5

**10. During the past 4 weeks, how much of the time has your physical health or emotional problems interfered with your social activities (like visiting with friends, relatives, etc.)?**

All of the time	Most of the time	Some of the time	A little of the time	None of the time
▼	▼	▼	▼	▼
 1	 2	 3	 4	 5

**11. How TRUE or FALSE is each of the following statements for you?**

Definitely true ▼	Mostly true ▼	Don't know ▼	Mostly false ▼	Definitely false ▼
-------------------------	---------------------	--------------------	----------------------	--------------------------

- a I seem to get sick a little easier than other people .....  1 .....  2 .....  3 .....  4 .....  5
- b I am as healthy as anybody I know .....  1 .....  2 .....  3 .....  4 .....  5
- c I expect my health to get worse .....  1 .....  2 .....  3 .....  4 .....  5
- d My health is excellent .....  1 .....  2 .....  3 .....  4 .....  5

***Thank you for completing these questions!***

## APPENDIX 6. ACTIVITIES OF DAILY LIVING

**II. ACTIVITIES OF DAILY LIVING** (increments of 0.5 may be used if strongly felt that a task falls between 2 scores)

**1. Speech**

- 0 - Normal
- 1 - Mildly affected. No difficulty being understood.
- 2 - Moderately affected. Sometimes asked to repeat statements.
- 3 - Severely affected. Frequently asked to repeat statements.
- 4 - Unintelligible most of the time.

**2. Swallowing**

- 0 - Normal.
- 1 - Rare choking (< once a month).
- 2 - Frequent choking (< once a week, > once a month).
- 3 - Requires modified food or chokes multiple times a week. Or patient avoids certain foods.
- 4 - Requires NG tube or gastrostomy feedings.

**3. Cutting Food and Handling Utensils**

- 0 - Normal.
- 1 - Somewhat slow and clumsy, but no help needed.
- 2 - Clumsy and slow, but can cut most foods with some help needed. Or needs assistance when in a hurry.
- 3 - Food must be cut by someone, but can still feed self slowly.
- 4 - Needs to be fed.

**4. Dressing**

- 0 - Normal.
- 1 - Somewhat slow, but no help needed.
- 2 - Occasional assistance with buttoning, getting arms in sleeves, etc. or has to modify activity in some way (e.g. Having to sit to get dressed; use velcro for shoes, stop wearing ties, etc.).
- 3 - Considerable help required, but can do some things alone.
- 4 - Helpless.

**5. Personal Hygiene**

- 0 - Normal.
- 1 - Somewhat slow, but no help needed.
- 2 - Very slow hygienic care or has need for devices such as special grab bars, tub bench, shower chair, etc.
- 3 - Requires personal help with washing, brushing teeth, combing hair or using toilet.
- 4 - Fully dependent

**6. Falling (assistive device = score 3)**

- 0- Normal.
- 1- Rare falling (< once a month).
- 2- Occasional falls (once a week to once a month).
- 3- Falls multiple times a week or requires device to prevent falls.
- 4- Unable to stand or walk.

**7. Walking (assistive device = score 3)**

- 0- Normal.
- 1- Mild difficulty, perception of imbalance.
- 2- Moderate difficulty, but requires little or no assistance.
- 3- Severe disturbance of walking, requires assistance or walking aids.
- 4- Cannot walk at all even with assistance (wheelchair bound).

**8. Quality of Sitting Position**

- 0- Normal.
- 1- Slight imbalance of the trunk, but needs no back support.
- 2- Unable to sit without back support.
- 3- Can sit only with extensive support (Geriatric chair, posy, etc.).
- 4- Unable to sit.

**9. Bladder Function (if using drugs for bladder, automatic score of 3)**

- 0- Normal.
- 1- Mild urinary hesitance, urgency or retention (< once a month).
- 2- Moderate hesitance, urgency, rare retention/incontinence (> once a month, but < once a week).
- 3- Frequent urinary incontinence (> once a week).
- 4- Loss of bladder function requiring intermittent catheterization/indwelling catheter.

**TOTAL ACTIVITIES OF DAILY LIVING SCORE:**

**APPENDIX 7. PATIENT GLOBAL IMPRESSION OF CHANGE**

The Patient Global Impression of Change is a 7-point scale that requires patients to assess how much their illness has improved or worsened relative to their baseline state at the beginning of the trial. Patients will self-rate their perceived change by completing the following statement: “Since I began trial treatment, my overall status is:”

1 = Very much improved

2 = Much improved

3 = Minimally improved

4 = No change

5 = Minimally worse

6 = Much worse

7 = Very much worse

## **APPENDIX 8. CLINICAL GLOBAL IMPRESSION OF CHANGE**

The Clinical Global Impression of Change is a 7-point scale that requires the clinician to assess how much the patient's illness has improved or worsened relative to a baseline state at the beginning of an intervention (Guy, 1976). The Clinician Global Impression of Change is assessed by completing the following statement “Compared to the patient’s condition at the start of the trial, this patient’s overall status is...”

1 = Very much improved

2 = Much improved

3 = Minimally improved

4 = No change

5 = Minimally worse

6 = Much worse

7 = Very much worse

## **APPENDIX 9. LOW-CONTRAST LETTER VISUAL ACUITY TEST (PART 1 ONLY)**

Due to the frequency of visual deficits in Friedreich's ataxia, assessment of visual function plays an important role in clinical trials and clinical practice. Vision testing is done using a portable retro-illuminated vision board. A pre-measured yellow vision string (full length is 3.2 meters, red mark denotes 2 meters) is used to measure the distance from the patient's forehead to the vision board. A pointer is also used to orient the patient to the specific line they are being asked to read.

Additional details regarding administration of the low-contrast visual acuity test will be provided in a study specific manual.

**APPENDIX 10. FATIGUE SEVERITY SCALE (PART 1 ONLY)**

**Fatigue Severity Scale (FSS, English version)\***

	
 strongly disagree strongly agree 
 
 
						
	1	2	3	4	5	6	7
1. My motivation is lower when I am fatigued.	0	0	0	0	0	0	0
2. Exercise brings on my fatigue.	0	0	0	0	0	0	0
3. I am easily fatigued.	0	0	0	0	0	0	0
4. Fatigue interferes with my physical functioning.	0	0	0	0	0	0	0
5. Fatigue causes frequent problems for me.	0	0	0	0	0	0	0
6. My fatigue prevents sustained physical functioning.	0	0	0	0	0	0	0
7. Fatigue interferes with carrying out certain duties and responsibilities.	0	0	0	0	0	0	0
8. Fatigue is among my three most disabling symptoms.	0	0	0	0	0	0	0
9. Fatigue interferes with my work, family, or social life.	0	0	0	0	0	0	0

*\*Patients are instructed to choose a number from 1 to 7 that indicates their degree of agreement with each statement where 1 indicates strongly disagree and 7, strongly agree. [Krupp et al, Arch Neurol 1989]*

[Redacted text block]

[REDACTED]

## APPENDIX 13. COVID-19 MITIGATIONS

This appendix outlines the mitigation strategies adopted to protect the health of participants in Study 408-C-1402, while maintaining compliance with good clinical practice (GCP) and minimizing the risk to trial integrity during the COVID-19 (Coronavirus Disease 2019) pandemic. At the time of the pandemic, Parts 1 and 2 of Study 408-C-1402 were already completed, therefore, this appendix applies to the extension phase of the study.

The mitigations specified below will be in place as long as COVID-19 related local government restrictions impact trial conduct, according to protocol specifications.

### 1. SITE OPERATIONS & PATIENT MANAGEMENT

If study sites are closed or restrict access to study teams during the COVID-19 pandemic, study teams must maintain open lines of communication with active study participants. Additionally, the Sponsor is to be regularly updated on changes to sites' status regarding closures, access limitations, contact information or other important information. Sites are encouraged to provide alternate contact information to their patients and the Sponsor. Updates are to be sent to the Sponsor study team [REDACTED].

### 2. COVID-19 TESTING AND INVESTIGATIONAL PRODUCT USE

If a patient enrolled in the Extension phase of Study 408-C-1402 tests positive for severe acute respiratory syndrome coronavirus 2 (SARS-CoV-2), the causative agent of COVID-19, the investigational product (IP) RTA-408 (omaveloxolone) must be temporarily discontinued until the patient no longer presents an active infection, as assessed by the Investigator and/or the patient's physician(s). The Sponsor must be notified immediately for additional guidance.

#### 2.1. Resumption of Investigational Product after Recovery from COVID-19 Infection

When the investigator deems that the patient can safely return to the site for an in-person visit, the investigator should conduct an unscheduled visit and perform all assessments as in Week 4. If there are no changes in clinical status that would preclude resuming IP, IP may be resumed. A follow-up telephone visit should be conducted 2 weeks after this unscheduled visit to collect adverse events and prior and concomitant medications. Four weeks after the unscheduled visit, the patient should return for repeat assessments as in the Week 4 visit. The usual visit schedule may resume thereafter.

### 3. INVESTIGATIONAL PRODUCT (IP) ACCESS

In order to maintain dosing continuity during the COVID-19 pandemic, IP may be directly shipped to the patient, using couriered tracking services, in cases where the patient becomes unable to travel to his/her study site. Stability information for IP shipments are contained in the "Guidance for Direct-to-Patient Shipping of RTA-408 Drug Product Capsules during the Coronavirus (COVID-19) Pandemic" ([Attachment 1](#)). All shipments must be sent via overnight express shipping (where possible) and include a temperature monitoring device. Sites will be supplied with temperature monitors upon request. For shipments that show temperature excursions below 20°C or above 25°C during transit, the Sponsor should be notified immediately via the COVID-19 Investigational Product Temperature Excursion form. The Sponsor will assess whether the product is deemed fit for use. During the assessment period, the patient should be informed to not take the IP until further notice from the site. IP dispensation should be

recorded in the appropriate drug accountability logs and all IP receipts of delivery should be filed in the Investigative Site File. If a patient is located in a country different from that of the site, the site will also provide information for customs on the shipped package.

#### 4. STUDY VISIT

Where in-person clinic visits are not possible, in-home visits and/or telemedicine visits (e.g. phone or video) may be conducted to complete study assessments not limited to:

- Adverse event assessment.
- Prior and concomitant medication assessment.
- Pregnancy testing for women of childbearing potential (WOCBP): patients must complete scheduled urine pregnancy tests at home. Pregnancy test(s) should be provided to patients where relevant. The site should obtain verbal confirmation from the patients that the test is negative prior to instructing the patients to start the shipped RTA-408 IP. Additionally, the site will specifically remind patients of the need to adhere to appropriate protocol required contraceptive measures where necessary.
- Vital signs.
- Safety labs: Every effort should be made to collect laboratory data using the central lab. Where use of the central lab is not possible, laboratory assessments should be collected through a local lab and reviewed by the investigator.

##### 4.1. United Kingdom Site

Per regulatory authority requirements, every effort should be made to obtain safety laboratory assessments every 24 weeks (Table 5) using either the central laboratory, local laboratories, or home health services (if available). In cases when laboratory assessments cannot be performed as a result of COVID-19 related restrictions, alternative proportionate mechanisms of oversight should be followed to ensure patient safety and well-being.

Specifically, alternative mechanisms of oversight to liver function and BNP tests were employed based on benefit/risk assessment in the context of the guidance for Investigators provided in the Investigator Brochure version 6.1, sections 6.2.1 – Transaminases and GGT Elevations, 6.6.2 – Transient Elevation of Serum Transaminases, and 6.6.1 – Fluid Overload.

For the six-monthly visits, the following alternative proportionate oversight approach should be followed:

- Telephone Questionnaire
  - Hepatic questions
    - Have you noticed any yellowing of your skin or eyes?
    - Have you noticed any usual swelling of your abdomen or feet?
    - Are you bruising very easily or had any cuts that kept bleeding?
    - Has your skin become itchy?
    - Have you had any changes in the color of your urine or stool?

- Have you had any pain in the right upper quadrant of your abdomen?
- Have you felt particularly nauseous?

Fluid overload/Cardiac questions

- Have you had any pain in your chest?
- Have you become more short of breath?
- Can you lie flat in bed without getting short of breath?
- Have you noticed your heart racing or going into a funny rhythm?
- Have you felt like you are going to faint? Or fainted?
- Additional hepatic recommendations
  - Continue site education regarding concomitant medication, particularly medications and/or supplements that are associated with hepatic injury including paracetamol.
  - Include urine bilirubin (if possible) with home urine dipstick.
- Home weight for fluid overload/cardiac assessments
  - Weight gain will be used to monitor fluid status.
  - Last home weight is used as baseline.
  - Patient(s) who experience a five-pound (2.3 kilograms) or greater increase in weight compared to the last home weight will be instructed to contact the site to assess the need to hold RTA-408 IP by the Investigator. IP should be discontinued if clinically important fluid retention is suspected.

Importantly, the alternative proportionate oversight measures outlined above can only be used for a certain period before safety laboratory assessments must be collected to conclusively measure relevant safety parameters. The maximum medically accepted delay in performing laboratory assessments (either local or on study) is 12 weeks post a six-monthly visit, assuming alternative proportionate oversight is ongoing and no concerns arise from this oversight.

If safety laboratory assessments cannot be completed within the maximum medically accepted delay, study drug must be temporarily discontinued until safety laboratory assessments can be obtained and it is deemed appropriate to restart IP dosing.

## ATTACHMENT 1

March 25, 2020

To: Clinical Program Operations  
Reata Pharmaceuticals, Inc.

From: Chemistry, Manufacturing & Controls / Quality Assurance  
Reata Pharmaceuticals, Inc.

Via E-mail Transmission

RE: Guidance for Direct-to-Patient Shipping of RTA-408 Drug Product Capsules during the Coronavirus (COVID-19) Pandemic

As a result of the coronavirus (COVID-19), certain adjustments have been made to ensure study patients receive their investigational product, on time, and consistently.

For clinical investigators, where patients are unable to travel outside of their home to the site, one adjustment being implemented is the shipping of investigational product directly to the patient, from the clinical investigator site.

As background, RTA 408 drug product 50 mg capsule kits (30ct, 3g desiccant, 75 mL bottle) have been assessed for stability following ICH guidelines for long term and accelerated conditions (25°C/60%RH & 40°C/75%RH). The results support the current labeled storage conditions of controlled room temperature, which is defined as 20°C to 25°C (68°F to 77°F), with brief excursions allowed to 15°C to 30°C (59°F to 86°F).

The stability results also provide supporting data to assess potential impact of short-term temperature excursions outside the labeled storage conditions. More specifically, for drug product capsule stored as a 30ct supply in 75 ml bottle with 3g desiccant, no changes in impurity profile were observed for 6 months for accelerated (40°C/75% RH) and 12 months for long term (25°C/60%RH) conditions.

**AVP, Product Development**

Printed: 

---

Signed: 

---

Date: 09 Oct 2019

This document describes the changes in the programs specified in the 408-C-1402 Part 2 statistical analysis plan (SAP) for sensitivity analyses using multiple imputation due to patient number sparseness at sites. This document is prepared prior to unblinding of the clinical and programming team and is considered to be a pre-specified, blinded modification algorithm in case programs fail to execute after unblinding due to sparse data at some sites.

The SAS procedure PROC MI may fail to impute if some sites have too few patients. However, it is possible that sparseness at site may lead to lack of convergence in other analyses. In the event data by site is too sparse for a given analysis to execute, the following covariates will be used in the order listed in place of site:

1. Region (USA/Non-USA) will be used instead of site.
2. If analyses will not execute with region (USA/Non-USA) then no covariates will be used to replace site.

For pes cavus population, no site or region will be included because there are fewer patients and few missing values.

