#### **14.3.2. Primary Efficacy Analysis**

Primary analysis of the efficacy data will be based on the ITT population. Mixed-model repeated measures (MMRM) analysis will be used to analyze the Part 1 and Part 2 primary and

secondary efficacy objectives. All scheduled efficacy values collected through the end of treatment visit (i.e., Week 12 in Part 1, Week 48 in Part 2) will contribute to the primary analysis. [REDACTED]

The dependent variable will be change from baseline. The model may include treatment, visit, and the interaction between treatment and visit as fixed effects; and visit will serve as a repeated measure. The SAP will specify the choice of variance-covariance structure and may specify additional covariates. The SAP may specify additional covariates. Procedures for handling missing data and appropriate sensitivity analyses will be described in the SAP for each study part.

Extension analysis of safety: As the extension is of an open-label design with no comparator group, all statistical analyses will be descriptive. The summary tables will be presented for the overall group of patients, and also split by previous treatment groups (i.e., RTA 408 or placebo).

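### Does the sparse-site note leave open, until after unblinding, which step of the multiple-imputation analysis loses site?

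*SAP*

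**What the plan says.** The available SAP text is a one-page note. It describes "changes in the programs specified in the 408-C-1402 Part 2 statistical analysis plan (SAP) for sensitivity analyses using multiple imputation". It was prepared before unblinding, for use "in case programs fail to execute after unblinding due to sparse data at some sites".

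The note names one procedure as vulnerable: "The SAS procedure PROC MI may fail to impute if some sites have too few patients". It then widens the warning: "it is possible that sparseness at site may lead to lack of convergence in other analyses". The rule follows: "In the event data by site is too sparse for a given analysis to execute, the following covariates will be used". Region (USA or non-USA) comes first, and after that "If analyses will not execute with region (USA/Non-USA) then no covariates will be used to replace site". One population is settled outright: "For pes cavus population, no site or region will be included because there are fewer patients and few missing values".

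Protocol section 14.3.2 offers treatment, visit and their interaction as fixed effects and passes the rest on: "The SAP will specify the choice of variance-covariance structure and may specify additional covariates". Neither text lists the covariates of the model fitted after imputation.

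**The concern.** A multiple-imputation analysis has two modelling steps: the imputation (PROC MI), and the model fitted to each completed dataset before pooling. Site could sit in either or both. The note fixes what replaces site and when, but never names the second step. If PROC MI fails with site while the second model would still run with site, one analyst might change PROC MI alone and another might change both.

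Failure is expected once treatment codes are open, so the choice might be made with results in view. It would also affect interpretation. If only PROC MI changes, the result differs from the primary through missing-data handling. If the second model changes too, much of any difference from a primary containing site comes from the covariate, and a reader could take it for sensitivity to missing data.

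**Working it through.** The note gives no figure to reproduce, so the check is a reading of the text followed by an illustration of size.

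**Reading the note in sequence.** The note says PROC MI may fail, then that *other* analyses may fail to converge. PROC MI is therefore counted as an analysis in its own right, separate from the rest. The rule applies when the data are too sparse for a *given* analysis to run. A model that runs has not met that condition.

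**Where the two readings part**, if both steps contain site:

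| PROC MI with site | Later model with site | Replace in failing step only | Replace throughout | Same? |
|---|---|---|---|---|
| runs | runs | no change | no change | yes |
| fails | fails | both change | both change | yes |
| fails | runs | PROC MI only | both | no |
| runs | fails | later model only | both | no |

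The last row is unlikely to arise from sparse sites, because the later model is fitted to completed data and has at least as many values per site as the imputation had. That leaves one row. If the later model has no site, that row disappears as well.

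**Inputs for size.** From the protocol: 100 patients (section 7.2), 1:1 allocation (7.1), at most about 20 centres (Synopsis), which is 100/20 = 5 patients per centre if spread evenly, and six post-baseline mFARS visits (11.2.1). Everything else is assumed, including site in the primary and post-imputation models.

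*Simulation A*: MMRM after imputation, 30 imputations, 400 trials per cell. Main cells: 10, 15 or 20 unequal sites, site share of variance 0 to 0.10, about 10% dropout under MAR, effect 0.5 SD. Differences are root mean square, in units of the primary SE.

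| Comparison | Difference (SE) | Opposite sides of p = 0.05 |
|---|---|---|
| Region in PROC MI only vs region in both steps | 0.23 to 0.42 | 10.1% |
| Primary with site vs PROC MI changed only | 0.07 to 0.09 | 2.8% |
| Primary with site vs both steps changed | 0.24 to 0.44 | 10.6% |
| Primary refitted with region vs both steps changed | 0.06 to 0.07 | 1.9% |

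The nine main cells hold 9 × 400 = 3,600 trials, so the Monte Carlo SE of 10.1% is √(0.101 × 0.899/3,600) = 0.5 percentage points. Mean estimates were 0.48 to 0.52 under both readings, against a true 0.5.

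*Simulation B*: ANCOVA after imputation with region in the imputation model, 11 or 20 sites, site share 0 to 0.15, 5% or 15% missing. The effect was set at 80% power for 50 per arm with assumed two-sided alpha 0.05: (1.96 + 0.84) × √(2/50) = 0.56 SD. Moving the later model from site to region or to nothing shifted the estimate by 0.21 to 0.42 SE on average. The verdict changed in 7% to 14% of trials.

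**Where the shift comes from.** In B, with no true site effect and 5% missing, the mean SEs with site and with region were 0.215 and 0.206 (11 sites), and 0.224 and 0.206 (20 sites). When the extra site terms carry only noise, the SD of the difference is roughly √(SE²site − SE²region), and its mean absolute value is 0.798 times that:

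- 11 sites: √(0.0462 − 0.0424) = 0.062; 0.798 × 0.062/0.215 = 0.23 SE, against 0.22 simulated.
- 20 sites: √(0.0502 − 0.0424) = 0.088; 0.798 × 0.088/0.224 = 0.31 SE, against 0.28 simulated.

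The shift is what dropping a many-level covariate produces by chance in 100 patients. It is not bias.

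**Pes cavus sentence.** It drops site and region without condition. The note's opening limits its subject to imputation, and the reason given, few missing values, bears mainly on imputation. The protocol's 20% cap means at most about 20 of 100 patients, so omitting site is sensible there.

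**The case for a change.** A document written to remove discretion after unblinding should leave none, and this one never says that a step which runs keeps its covariates. Two simulations of different design agree that the choice moves the estimate by about 0.2 to 0.4 SE. Changing both steps also raises disagreement with a site-adjusted primary from 2.8% to 10.6%, nearly all of it due to the covariate, since matching covariates brings it back to 1.9%. One sentence would settle the matter.

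Part of this stands. The explicit sentence is absent, and a reader of the results will need to know which covariates each step used. The rest is weaker. The sentence one would add, replacing site only where execution fails, restates what the note already implies. The 10% figure does not measure risk in this trial: the fallback was imposed on every simulated trial, the chance of its being needed is not estimated, and the percentage depends on the assumed effect. A sensitivity analysis is also read mainly for whether the estimate is consistent with the primary, and less for which side of 0.05 it falls on.

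**Conclusion.** No change is needed. The note fixes the order and a mechanical trigger before unblinding, and its wording favours replacing site only in the analysis that cannot run. Followed as written, it gives a sound sensitivity analysis. The other reading also gives a valid estimate.

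What remains is a missing detail in one narrow case: PROC MI fails with site while a later model containing site still runs. There the readings differ by about 0.2 to 0.4 SE under assumed site numbers, site variation, dropout and effect. The primary result, its type I error and the fallback order are unaffected.

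This rests on two things the available documents cannot settle: whether the post-imputation model contains site (if not, the point vanishes), and how likely PROC MI is to fail. Neither would turn the gap into an error. The pes cavus sentence is clear enough from its context and stated reason.
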